## Study Population

Adults (>18 years) who are currently receiving treatment for SUD in the outpatient treatment program at West Virginia University Chestnut Ridge Center (WVUCRC) (n = 340 approx.).

Inclusion criteria are patients diagnosed with SUD who have completed intensive acute phase 1 treatment, and who desire to pursue continuous recovery phases (per facility protocol). All participants must be alert and oriented, provide written consent, and be able to read and write English.

[figure not shown]
Exclusion criteria are patients diagnosed with severe mental illness (who cannot consent to participate), have a medical history of asthma or other serious respiratory disease, and known allergy to citrus. There are no exclusion criteria for gender, race, and/or ethnicity.

Anyone who meets inclusion criteria in the sample population is invited to participate. I am advertising throughout entire population of the study.

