### **Plus, the following**

#### **Data will be collected from the chart and from survey (self-report)**

1. Identifier variables of Comfort, Ease, and Stress
2. Stage of treatment in the SUD treatment program (Chart)
3. Presence of anxiety and/or depression (Chart)
4. Presence of severe mental illness Dx (Chart)
5. Allergies to citrus fruits such as grapefruit, lemon, orange, or bergamot (Chart and self report)

6. Previous experience with any integrative or complementary therapies such as yoga, massage, acupuncture, aromatherapy with essential oils, herbal preparations, meditation, mindfulness practices (Self-report)
7. Pregnant and/or nursing (Self-report)
8. Severe breathing problems such as asthma, chronic bronchitis, or COPD (Chart and self-report)
9. Report of sense of smell (self-report)
10. Dx of a problem with sense of smell (Chart and self-report)
11. Current illness with cold, flu, or covid (Self-report)

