## Prior to opening a Study Packet

1. In a private location, Enroller will determine eligibility for this study.
  - a. Inclusion criteria are as follows:
    - i. Older than 18 years of age
    - ii. Currently enrolled in treatment
    - iii. Have completed intensive phase 1 and wish to continue with treatment
    - iv. Alert & oriented
    - v. Able to provide written consent
    - vi. Able to read & write English
  - b. Exclusion criteria are as follows:
    - i. Diagnosed with severe mental illness
    - ii. Medical history of asthma
    - iii. Other serious respiratory disease
    - iv. Known allergy to citrus
2. In a private location, Enroller will prescreen using created survey tool (appendix A)
  - a. Use the prescreening survey provided
  - b. Read prescreening survey to participants and record answers
  - c. If not contraindicated by prescreening questions, allow participant to smell the aroma inhaler (3 inches from nose)
    - i. Record all reactions, “liked the smell”, “sneezed”, “said ‘yuck’” on the presurvey. Record “no negative reactions” as applicable (This is a vital component of aromatic research)
3. IF PARTICIPANT IS INELIGIBLE, thank them for their time, note on MLS that they were screened and why they were ineligible. Use the special section at the end of the MLS to make this notation. Do not use an Id # space. Write “ineligible” and the date across the top of the survey.
4. IF PARTICIPANT IS ELIGIBLE, file prescreening form in predetermined place and obtain a study packet in the order they are arranged (001-098)
  - a. Enter date and name of participant on the **Random Number Table (RNT)** sheet
5. Record Unique Identifier packet number on **Master Log Sheet (MLS)**
  - a. Use MLS to track Participants
  - b. This Unique Identifier number is already on every document in each packet

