## Appendix A

### PRESCREEN SURVEY

#### To be completed by the Enroller:

1. Please answer the following questions about aversion (dislike) or allergy.
  - a. Do you have a strong aversion to smells of citrus and/or citrus fruit(s) themselves (such as grapefruit, orange, lemon, or bergamot). Yes/No (If no, please go to the next question)
    - i. Do you have any allergies to citrus? Yes/No (If no, answer next question)
    - ii. This study uses the pure essential oil of Bergamot. Have you ever smelled this fruit or essential oil? Yes/No
    - iii. If yes, you have smelled Bergamot fruit or essential oil, do you dislike the smell? Yes/No
    - iv. If yes, you dislike the smell of Bergamot essential oil, you are excused from participation in this study.

If yes, you have a strong dislike or allergy to Bergamot fruit or essential oil, you are not eligible to participate in this study.

If no strong aversion or allergy to Bergamot, proceed with the following questions.

2. Do you or have you ever been told by a doctor that you have any of the following medical or health conditions? Yes/No (If No, go to question 3)
  - a.  Severe breathing problems such as asthma, chronic bronchitis, or a chronic obstructive pulmonary disease (COPD)
  - b.  Pregnant or the possibility of becoming pregnant and/or breastfeeding
  - c.  Allergies to citrus fruits such as grapefruit, lemon, orange, or bergamot

If yes to any responses to question 2, you are not eligible to participate in this study.

3. Have you ever tried any integrative or complementary therapies (examples include; massage, yoga, acupuncture, aromatherapy with essential oils, herbs, meditation, mindfulness practices etc.) Yes/No (If Yes, please answer the following. If No, go to question 5)
  - a. If yes, list which ones? \_\_\_\_\_
  - b. If yes, what was your main reason for using complementary therapies? Choose all that apply
    - i.  Pain
    - ii.  Anxiety
    - iii.  Relaxation
    - iv.  Stress relief

v. Other, please write in \_\_\_\_\_

c. If there is a specific therapy used for a specific symptom, please write the therapy beside the symptom listed above.

d. On a scale of 0 to 10 with 0 being not at all effective and 10 being very effective, how effective was the therapy noted above for relief of the symptom? (Example: Pain, massage, 7/10)

4. Was one of the complementary therapies you have tried aromatherapy or essential oils? Yes/No (If Yes, please answer the following. If No, go to question 5)

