- No, I have not used aromatherapy or essential oils. (Proceed to question 5)
- Yes, I have used essential oils and have tried (please list the essential oils you have tried) \_\_\_\_\_
- Of those essential oils you have tried, which one or ones would you consider to be your favorite(s) \_\_\_\_\_
- Of those essential oils you have tried, which one or ones would you consider to be your least favorite(s) \_\_\_\_\_
- Have you ever tried Bergamot essential oil? Yes/ No
  - If yes, why did you try it? \_\_\_\_\_  
If yes, what, if any effect, did you think it had? \_\_\_\_\_

5. Do you have difficulty smelling or recognizing odors? Yes/No

- If yes, do you think your problems with smelling are because of allergies or stuffy nose and congested sinuses? Yes/No
  - Are you currently feeling sick with a cold, the flu, or with COVID? Yes/No
- If yes, you have problems with your sense of smell, have you ever been *told by a doctor* that you have a problem with your sense of smell? Yes/No
  - If yes, have you ever been diagnosed or told by a doctor that you have *anosmia*, which is a total loss of the sense of smell? Yes/No
    - Was this loss of smell related to COVID or some other illness? Yes/No

If yes, approximately when did the loss of smell begin \_\_\_\_\_

END OF SURVEY

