**Participant is not eligible to participate in this study**

If they answered "Yes" to either or both of the following questions:

Question 1. "I am allergic to or have a strong aversion to smells of citrus and/or citrus fruit(s) themselves (such as grapefruit, orange, lemon, bergamot)"

Question 2. "Do you or have you ever been told by a doctor that you have any of the following medical or health conditions", and/or

**ENROLLER: Record all reactions to the smell of Bergamot during prescreening. If no negative reaction, write "No negative reaction" \_\_\_\_\_**

**Once complete, either excuse participant if they are not eligible or proceed by obtaining a packet and opening study materials.**

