## POST SURVEY

Please answer the following regarding the intensity or strength of the aroma inhaler.

1. On a scale of 1 to 10 rate overall how enjoyable the aroma of the inhaler was (0 being not enjoyable at all and 10 being very enjoyable)

0	1	2	3	4	5	6	7	8	9	10
---	---	---	---	---	---	---	---	---	---	----

2. On a scale of 1 to 10 rate the usual strength smell of the aroma inhaler (0 being no strength and very weak to 10 the strongest it could be)

0	1	2	3	4	5	6	7	8	9	10
---	---	---	---	---	---	---	---	---	---	----

3. How likely are you to continue to use this aroma inhaler (1 being not at all likely and 10 being very likely)?

0	1	2	3	4	5	6	7	8	9	10
---	---	---	---	---	---	---	---	---	---	----

4. Any other thoughts you wish to share about this experience?

Thank you for taking the time to complete this study, please return this and all other surveys and the logbook in the prepaid envelope. Once this is received, a gift card will be sent. If you have any further questions, please contact [name] at [[contact]](mailto:[contact])

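### Smell loss is asked about at prescreen, but no eligibility rule or analysis uses the answer, so people with diagnosed anosmia may be randomised in an aroma trial

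*Combined protocol and SAP*

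**What the plan says.** **What is asked.** Question 5 of the Prescreen Survey (Appendix A) opens with "Do you have difficulty smelling or recognizing odors? Yes/No". A Yes leads to two branches. One asks whether allergies or congestion explain the difficulty and contains "Are you currently feeling sick with a cold, the flu, or with COVID? Yes/No". The other asks about a doctor-reported smell problem and then about anosmia, which the form explains as complete loss of smell. The survey ends there. Separately, the data list under Informed Consent Process includes "Dx of a problem with sense of smell (Chart and self-report".

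**What excludes.** Question 2 carries its own stop rule: "If yes to any responses to question 2, you are not eligible to participate in this study". The box after the survey makes a person ineligible for a Yes "to either or both of the following questions", and the two it lists are questions 1 and 2. Under Study Population, the exclusions are severe mental illness and people who "have a medical history of asthma or other serious respiratory disease, and known allergy to citrus". The list under Prior to opening a Study Packet gives the same conditions. Neither list mentions smell.

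**The sniff.** The enroller is told: "If not contraindicated by prescreening questions, allow participant to smell the aroma inhaler (3 inches from nose". Reactions are written down, but nobody is required to detect the aroma.

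**What is analysed.** The Statistical Analysis Plan names repeated measures ANOVA, paired t-tests, Fisher's exact test and correlations. It has no covariate, subgroup or sensitivity analysis by smell function. The Post Survey asks participants how enjoyable the aroma was and to "rate the usual strength smell of the aroma inhaler".

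**The concern.** The intervention is an aroma, delivered by an inhaler and defined as aromatherapy in the Common Terms List. Someone who cannot perceive it plausibly receives less of the intervention than the trial means to test.

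Two things are at stake:

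- **Aim 1.** Any such participants in the inhaler arm would pull the difference in comfort, ease and stress towards zero. Randomisation still protects against bias between arms. What is lost is sensitivity, in a sample size that states no allowance for dropout or non-response.
- **Aim 2.** Ratings of enjoyment and strength from someone who cannot smell mix a property of the rater with a property of the product. Adherence is taken from logbook entries, so the same person could count as fully adherent.

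The plan already collects what it needs to deal with this. If it stays silent, any look at smell function after a null result would be post hoc.

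**Working it through.** **1. Can a person with anosmia pass every gate as written?**

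| Step | What it does with smell loss |
|---|---|
| Study Population exclusions | not mentioned |
| Exclusions under Prior to opening a Study Packet | not mentioned |
| Prescreen questions 1 and 2 | ask about aversion, allergy and medical conditions; each carries a stop rule |
| Prescreen question 5 | asks about it; no instruction |
| Ineligibility box | lists questions 1 and 2 only |
| Sniff test | records reactions; someone who smells nothing can be entered as having no negative reaction |
| Statistical Analysis Plan | answers not used |

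Nothing in this chain stops that person. The 2022 amendment letter (Appendix G) has materials mailed and the sniff done at home, which makes the verbal question more important as an early check.

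**2. Reproduce the planned sample size.** Inputs from Sample Size: f = 0.25, alpha = 0.05, power 80%, two groups, m = 2 measurements, correlation rho = 0.50, N = 98 (49 per arm). The G*Power between-factors form of repeated measures ANOVA uses a noncentral F with 1 and N − 2 degrees of freedom and

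lambda = f² × N × m / (1 + (m − 1) × rho) = 0.0625 × 98 × 2 / 1.5 = 8.167.

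This gives power 0.808, and N = 98 is the smallest even total reaching 80%, so the stated figure reproduces. The within-between interaction form at f = 0.25 gives N = 34 and does not match.

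**3. Dilution.** Prevalence is not in the documents, so let q be an assumed share of the inhaler arm that cannot smell. Assume also that these people gain nothing. The mean effect becomes f(1 − q), and lambda becomes 8.167 × (1 − q)².

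| q | People per inhaler arm (49q) | f(1 − q) | lambda | Power at N = 98 | N for 80% |
|---|---|---|---|---|---|
| 0 | 0 | 0.250 | 8.167 | 0.808 | 98 |
| 1% | 0.5 | 0.2475 | 8.004 | 0.800 | 100 |
| 5% | 2.5 | 0.2375 | 7.370 | 0.767 | 108 |
| 10% | 4.9 | 0.225 | 6.615 | 0.721 | 120 |

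**4. Sensitivity to the assumptions.**

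- *Partial effect.* If people without smell keep half the benefit, q = 10% gives f = 0.25 × (1 − 0.10 × 0.5) = 0.2375. That is the 5% row, with power 0.767.
- *Extra spread.* The table ignores the added variance from mixing responders and non-responders. With d = 2f = 0.5 and q = 10%, the inhaler arm gains 0.10 × 0.90 × 0.5² = 0.0225. Averaged over both arms that is 0.01125, on a variance of (1 + 0.5)/2 = 0.75 for the two-visit mean. Lambda falls to 6.615 × 0.75/0.76125 = 6.517 and power to about 0.715, a small change.
- *Choice of test.* If the 0.5 SD difference exists only after treatment and is tested as group by time, power at N = 98 is 0.688 undiluted, 0.643 at 5% and 0.597 at 10%. The starting level differs, but the loss is of similar size.

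**The case against.** **Entry is permitted, not shown.** A reader might infer that people who cannot smell did enter and did dilute the effect. The documents only leave the door open. This objection stands.

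**Zero effect is an assumption.** The Common Terms List and Background describe oil constituents acting on nerve receptors. The logbook instructions also include paced inhaling, breath-holding and exhaling, which the control logbook does not ask for. Some benefit without smell is plausible, so the power losses in the table are best read as an approximate upper bound. This stands too.

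**A Yes to question 5 is not anosmia.** It covers a stuffy nose and congestion. Treating every Yes as being unable to smell would go beyond the form. Nor does the prescreen identify everyone with a cold, flu or COVID, because that item is reached only after a Yes to smell difficulty. Both points stand and narrow the fix.

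**The ratings are not worthless.** The strength scale has a zero for no strength, which someone who smells little can validly choose. If broad entry is intended, that answer says something about acceptability. This stands against calling the ratings meaningless. It does not remove the difficulty of interpreting a pooled average.

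**A rule may be missing from the text.** The ineligibility box ends on a dangling conjunction, and the participant-time table describes six prescreen questions where five are numbered. The consent pages are not available. A further rule may have been intended, but none appears in the available text, and the gap would need closing either way.

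**This is a small matter in a pilot.** At 5% it concerns two or three people in the inhaler arm and about four points of power. That limits its weight, but the remedy costs very little.

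**Conclusion.** The point holds in a limited form. The plan asks about diagnosed anosmia and collects smell diagnosis, then uses neither for eligibility nor for analysis. People with total loss of smell may therefore be randomised and asked to rate an aroma.

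The effect on power is modest and conditional. From 0.808, it falls to about 0.800, 0.767 or 0.721 at assumed shares of 1%, 5% or 10%, and by less if any benefit survives without smell. These figures rest on an assumed prevalence, zero effect without smell, and the between-groups test that reproduces N = 98. Even a 1% share uses up the margin above 80%.

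The documents do not support a claim that dilution occurred, that all who report smell difficulty are affected, or that the comparison between arms is biased. The point is worth acting on because the item is already asked, before any packet is assigned.

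**What to change.** **Preferred.** Add diagnosed anosmia, using the nested item already in question 5, to the exclusions in all three places: Study Population, the list under Prior to opening a Study Packet, and the ineligibility box after the Prescreen Survey. Changing only some of them would create a new inconsistency. Apply the rule before a packet is assigned, so that it falls equally on both arms and leaves the randomised comparison intact. Complete the unfinished sentence in the box at the same time. The cost is one criterion line and a slightly smaller eligible pool.

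**If broad entry is intended.** Say so, and pre-specify in the Statistical Analysis Plan one sensitivity analysis of the Aim 1 outcomes and the Post Survey ratings that omits participants with diagnosed anosmia, applied to both arms. Do not drop everyone who answers Yes to question 5, since that would also remove people with ordinary congestion. This needs no new data.

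**Optional.** Deferring people with a current cold, flu or COVID is a choice for the study team. It would require asking that item of everyone, because it now sits beneath a Yes to smell difficulty.

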**Participant is not eligible to participate in this study**

If they answered "Yes" to either or both of the following questions:

Question 1. "I am allergic to or have a strong aversion to smells of citrus and/or citrus fruit(s) themselves (such as grapefruit, orange, lemon, bergamot)"

Question 2. "Do you or have you ever been told by a doctor that you have any of the following medical or health conditions", and/or

**ENROLLER: Record all reactions to the smell of Bergamot during prescreening. If no negative reaction, write "No negative reaction" \_\_\_\_\_**

**Once complete, either excuse participant if they are not eligible or proceed by obtaining a packet and opening study materials.**

## COMFORT SURVEY

Thank you VERY MUCH for helping us understand your **comfort**. Below are statements that relate to your comfort right now. Six numbers are provided for each question; please circle the number you think most closely matches your feeling. Your responses should describe your comfort right now.

	Right now...	Strongly Disagree			Strongly Agree	
1.	My body is relaxed right now	1	2	3	4	5
2.	I feel useful because I am working hard	1	2	3	4	5
3.	There are those I can depend on when I need help	1	2	3	4	5
4.	My condition gets me down	1	2	3	4	5
M5.	I feel confident	1	2	3	4	5
6.	I feel dependent on others	1	2	3	4	5
7.	I feel my life is worthwhile right now	1	2	3	4	5
8.	I am inspired by knowing that I am loved	1	2	3	4	5
9.	No one understands me	1	2	3	4	5
10.	My pain is difficult to endure	1	2	3	4	5
11.	I am inspired to do my best	1	2	3	4	5
12.	I am unhappy when I am alone	1	2	3	4	5
13.	My faith helps me not to be afraid	1	2	3	4	5
14.	I do not feel healthy right now	1	2	3	4	5
15.	I am afraid of what is next	1	2	3	4	5
16.	I am being treated fairly	1	2	3	4	5
17.	I have experienced changes which make me feel uneasy	1	2	3	4	5
18.	I am very tired	1	2	3	4	5
19.	I can rise above my pain	1	2	3	4	5
20.	The mood around here uplifts me	1	2	3	4	5
21.	I am content	1	2	3	4	5

22.	My beliefs give me peace of mind	1	2	3	4	5	6
23.	I feel out of control	1	2	3	4	5	6
24.	I feel safe	1	2	3	4	5	6
25.	I feel peaceful	1	2	3	4	5	6
26.	I am depressed	1	2	3	4	5	6
27.	I have found meaning in my life	1	2	3	4	5	6
28.	I need to feel good again	1	2	3	4	5	6

## EASE MEASURE

**Ease Measure:** Please circle the number (**never; sometimes; frequently; always**) to indicate your degree of agreement with each statement as a descriptor of what is generally happening in your everyday life.

		Never	Sometimes	Frequently	Always
1.	I can let go of my daily stress.	1	2	3	4
2.	I am comfortable in knowing what to do when in a difficult situation.	1	2	3	4
3.	I feel comfort when I share my everyday experiences.	1	2	3	4
4.	I am at peace with myself.	1	2	3	4
5.	I can handle situations in a calm manner.	1	2	3	4
6.	I struggle to get though my day.	1	2	3	4
7.	I can go to a place of tranquility when needed.	1	2	3	4
8.	I accept things I cannot change.	1	2	3	4
9.	I take time to rest during my busy day.	1	2	3	4
10.	I feel safe.	1	2	3	4
11.	I am content with my life.	1	2	3	4
12.	I experience moments of joy.	1	2	3	4

13. I take time for soothing activities.	1	2	3	4
14. I am uncomfortable in everyday situations.	1	2	3	4
15. I have sadness during my day.	1	2	3	4
16. I am nervous during everyday circumstances.	1	2	3	4
17. I worry about what is happening in my life.	1	2	3	4
18. I experience my day going smoothly.	1	2	3	4
19. I can let go of restrictive circumstances.	1	2	3	4
20. I have energy to face whatever comes my way.	1	2	3	4

## STRESS SURVEY

Please read each statement and circle a number 0, 1, 2, or 3, which indicates how much this statement applied to you over the past week. There are no right or wrong answers. Do not spend too much time on any statement.

The rating scale is as follows:

0 Did not apply to me at all

1 Applied to me to some degree, so some of the time

2 Applied to me to a considerable degree or a good part of the time

3 Applied to me very much or most of the time

1. I find it hard to wind down	0	1	2	3
2. I was aware of my dry mouth	0	1	2	3
3. I couldn't seem to experience any positive feelings at all	0	1	2	3
4. I experienced breathing difficulty (e.g. excessively rapid breathing, breathlessness in the absence of physical exertion)	0	1	2	3
5. I found it difficult to work up the initiative to do things	0	1	2	3
6. I tend to over-react to situations	0	1	2	3
7. I experienced trembling (e.g. in the hands)	0	1	2	3

8. I felt that I was using a lot of nervous energy	0	1	2	3
9. I was worried about situations where I might panic and make a fool of myself	0	1	2	3
10. I felt that I had nothing to look forward to	0	1	2	3
11. I found myself getting agitated	0	1	2	3
12. I found it difficult to relax	0	1	2	3
13. I felt down-hearted and blue	0	1	2	3
14. I was intolerant of anything that kept me from getting on with what I was doing	0	1	2	3
15. I felt I was close to panic	0	1	2	3
16. I was unable to become enthusiastic about anything	0	1	2	3
17. I felt I wasn't worth much as a person	0	1	2	3
18. I felt that I was rather touchy	0	1	2	3
19. I was aware of the action of my heart in the absence of physical exertion (e.g. sense of heart rate increase, heart missing a beat)	0	1	2	3
20. I felt scared without any good reason	0	1	2	3
21. I felt that life was meaningless	0	1	2	3

